6.3.3 Exploratory Efficacy Endpoints

All endpoints listed as primary and secondary will also be analyzed separately within the subset of patients with wild-type p53.

The following exploratory efficacy endpoints will also be assessed:

- MRD response over time (i.e., during induction, consolidation, and maintenance)
- Time to MRD-negative status, defined as time from initiation of treatment to confirmation of negative MRD status

Patients with continuing MRD positive status at the time of analysis will be censored at the date of last MRD assessment. Patients with no post baseline MRD assessment will be censored at Day 1.

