3.1.4 Post-Treatment Follow-Up and Survival Follow-Up

Patients who complete treatment or discontinue treatment for reasons other than disease progression will undergo assessments (see [Appendix 1](#)) during the post-treatment follow-up period, which will continue until morphologic relapse or up to 2 years, whichever occurs first. Patients who experience morphologic relapse or were followed for 2 years in the post-treatment phase will be evaluated for survival status and

initiation of new anti-leukemia treatment until the end of the study. Details are provided in the schedules of activities (see [Appendix 1](#)).

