4.5.6 Tumor and Response Evaluations

Hematologic malignancy response will be assessed according to ELN and additional response criteria for AML (see [Appendix 19](#)).

Hematologic malignancy response assessments (HMRA) require sampling of blood and bone marrow on the same day as indicated (a window of 4 days is acceptable between the blood and bone marrow sampling). Bone marrow aspirates are required, but if bone marrow biopsies are performed, the biopsy results should be provided along with the aspirate. Depending on the timepoint in the schedule of activities, the HMRA is established on the basis of blood counts only, or includes the assessment of bone marrow. Patients will be considered to be in their best response state until definitive evidence of relapse is available from blood counts, bone marrow aspirate, or bone marrow biopsy.

In the event that a bone marrow aspirate or biopsy is equivocal (i.e., a recovering marrow), the bone marrow assessment and complete blood count should be repeated > 7 days later.

In case disease progression/relapse is determined solely by symptomatic deterioration or by a hematology assessment, a bone marrow aspirate should be performed at that time to complete HMRA. If a patient progresses or relapses outside of the scheduled visit, an unscheduled HMRA must be provided.

If a bone marrow aspirate is performed at any unscheduled timepoint during the study, an unscheduled HMRA must be provided.

Please note that at the time of bone marrow sampling for HMRA, the bone marrow sample collected (aspirate) should also allow for further analyses (e.g., MRD by flow cytometry, MRD by NGS) and the amount taken should be taken into consideration.

During the treatment period, HMRA are to be performed and reviewed before the start of a new treatment cycle. In the event that a patient has a dosing delay > 7 days in consolidation or induction, weekly blood counts must be performed for HMRA to

document evidence of non-progression. Treatment failure and relapse will lead to discontinuation of the study medication and patients will enter follow-up (see [Appendix 1](#)).

During the follow-up of patients who remain in remission after treatment, blood will be required every month and a bone marrow aspirate will be required every 6 months to allow for HMRA until relapse. Refer to [Appendix 1](#) for further details.

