4.5.8.1 MRD Assessments for Patients in the Post-Consolidation Phase

Patients in the post-consolidation phase with an MRD-positive remission after induction will be enrolled after local MRD assessment with a validated quantitative AML specific method. In order to monitor MRD during maintenance, assessments will be performed at 3 monthly intervals (see [Appendix 1](#)).

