6.3.2 Secondary Efficacy Endpoints

The following secondary efficacy endpoints will be analyzed in patients enrolled during specified phases through use of the same methods described for the primary efficacy endpoint:

Dose-escalation or expansion phase

- Proportion of patients with a CR, CRi, or CRp at the end of induction treatment
- Proportion of patients with a CR or CRh at the end of induction treatment
- Proportion of patients with a negative MRD status at the end of induction treatment

Post-consolidation phase

- Proportion of patients converting from MRD-positive to MRD-negative status at any time during treatment

The following secondary efficacy endpoints will be analyzed in patients enrolled during the dose-escalation and expansion phases:

- EFS, defined as the time from initiation of study treatment (for post-consolidation patients, date of initiation of induction treatment prior to this study) to treatment

failure (failure to achieve CR, CRi, CRp, or CRh), hematologic relapse, or death from any cause, whichever occurs first

Patients with no EFS event at the time of analysis will be censored at the date of last response assessment. Patients with no EFS event and no postbaseline response assessment will be censored at Day 1.

- OS, defined as the time from initiation of study treatment to death from any cause
Patients who have not died at the time of analysis will be censored at the date the patient was last known to be alive.
- RFS in patients who achieve remission (CR, CRi, CRp, or CRh), defined as the time from remission to the date of hematologic relapse or death from any cause, whichever occurs first
Patients with no RFS event at the time of analysis will be censored at the date of last response assessment.

The following secondary efficacy endpoints will be analyzed in patients enrolled during the post-consolidation phase:

- EFS, defined as the time from initiation of induction treatment (prior to study entry) to hematologic relapse or death from any cause, whichever occurs first
Patients with no EFS event at the time of analysis will be censored at the date of last response assessment. Patients with no EFS event and no postbaseline response assessment will be censored at Day 1.
- OS, defined as the time from remission (prior to study entry) to death from any cause
Patients who have not died at the time of analysis will be censored at the date the patient was last known to be alive.

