- RFS in patients who achieved remission (CR, CRi, CRp, or CRh), defined as the time from remission (prior to study entry) to the date of hematologic relapse or death from any cause, whichever occurs first
Patients with no RFS event at the time of analysis will be censored at the date of last response assessment.

The following secondary efficacy endpoint will be analyzed in patients enrolled during all phases:

- Change from baseline in patient-reported disease-related symptoms and health-related quality of life at specified timepoints, as assessed through use of the FACIT-Fatigue, EORTC QLQ-C30 (selected scales), and EORTC Item Library (selected symptoms)

EFS, OS, and RFS will be analyzed descriptively using the Kaplan–Meier method (Kaplan and Meier 1958).

Where medians are reached, the corresponding estimated median will be provided, along with the 95% CI by means of the Brookmeyer and Crowley method (Brookmeyer and Crowley 1982). In addition, when available at the time of the analysis, landmark estimates of the proportion of patients who are event free at 6 months, 9 months, 1 year, and 2 years will be provided, along with 95% asymptotic CIs using Greenwood's formula for standard errors.

Descriptive summary statistics and change from baseline will be calculated at each assessment timepoint for the FACIT-Fatigue, EORTC QLQ-C30 scales, and EORTC Item Library symptoms. Further details of the PRO analyses will be provided in the Statistical Analysis Plan.

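### Time to MRD-negative status censors patients who die or relapse while MRD positive, so a survival-type estimate overstates the probability of converting

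*Combined protocol and SAP*

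**What the plan says.** Section 6.3.3 defines the endpoint as "Time to MRD-negative status, defined as time from initiation of treatment to confirmation of negative MRD status". Two rules follow: "Patients with continuing MRD positive status at the time of analysis will be censored at the date of last MRD assessment" and "Patients with no post baseline MRD assessment will be censored at Day 1". No rule covers a patient who dies or relapses before becoming MRD negative, and no estimator is named.

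Four other places bear on this:

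- Section 6.3.2 names an estimator for three other endpoints: "EFS, OS, and RFS will be analyzed descriptively using the Kaplan–Meier method". It defers only the patient-reported outcome details to a separate plan.
- In the dose-escalation and expansion phases, EFS runs to treatment "failure (failure to achieve CR, CRi, CRp, or CRh), hematologic relapse, or death from any cause, whichever occurs first". There the same occurrences are events.
- Section 4.5.6 states: "Treatment failure and relapse will lead to discontinuation of the study medication and patients will enter follow-up". Section 3.1.4 adds: "Patients who experience morphologic relapse or were followed for 2 years in the post-treatment phase will be evaluated for survival status". No MRD sampling is scheduled in that survival follow-up (Appendix 1, Table 5).
- Section 6.3.1 counts patients with no post-baseline assessment as non-responders for CR, and Section 6.3 puts every treated patient in the efficacy analyses.

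**The concern.** Censoring is harmless when the censored patient has the same future chance of the event as those still at risk. A patient who has died has none. A relapsed patient has stopped study drug and moves to survival follow-up, so has practically no chance of converting on study. With no other instruction, both are coded like a patient who is well, still on treatment and waiting for the next marrow. The estimate then hands their share of probability to later converters.

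The Day 1 rule adds to this. The first scheduled post-baseline marrow in induction is on Day 28 (Appendix 1, Table 1). A patient who dies before it never enters the risk set at any conversion time, although the CR analysis keeps the same patient as a failure.

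At stake is a conversion curve that lies above the proportion who actually became MRD negative, with a median that is too early. It would be reported beside secondary MRD proportions in the same small cohorts, with nothing in the plan to explain the gap.

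**Working it through.** The plan gives no estimate, power or sample size for this endpoint, so there is no figure to reproduce. The cohort sizes (30 post-consolidation, 20 per expansion cohort) and the post-consolidation MRD schedule, where "assessments will be performed at 3 monthly intervals", come from the documents. All event counts and rates below are assumptions.

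**Discrete examples.** At each marrow visit the Kaplan-Meier factor is 1 − conversions/at risk. Patients who die or relapse leave the risk set after their last MRD visit, as the rule directs. With no other censoring, the cumulative incidence is conversions divided by all treated patients.

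Post-consolidation, N = 30, conversions 4, 3, 2, 1 at four successive visits. Cumulative incidence: 10/30 = 33.3%.

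- One death or relapse after each of the first three visits: 1 − (26/30)(22/25)(19/21)(17/18) = 34.8%.
- Three after each: 1 − (26/30)(20/23)(15/17)(11/12) = 39.0%.
- Three after each, plus 2 patients who die unsampled and are censored at Day 1: 1 − (24/28)(18/21)(13/15)(9/10) = 42.7%.
- Heavy attrition (5, 5, 3, plus 2 at Day 1): 1 − (24/28)(16/19)(9/11)(5/6) = 50.8%.

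Expansion cohort, N = 20, conversions 7, 2, 1, 1, with 1, 3, 1, 1 competing events after those visits. Cumulative incidence: 11/20 = 55.0%.

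- No early deaths: 1 − (13/20)(10/12)(6/7)(4/5) = 62.9%.
- Two early deaths censored at Day 1: 1 − (11/18)(8/10)(4/5)(2/3) = 73.9%.

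**Constant hazards over 12 months.** Let c be net conversion, the value that one minus Kaplan-Meier estimates, and d the net probability of a competing event. The hazards per 12 months are hc = −ln(1 − c) and hd = −ln(1 − d). The cumulative incidence is [hc/(hc + hd)] × [1 − exp(−(hc + hd))].

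For c = 50% and d = 30%: hc = 0.693 and hd = 0.357, so the cumulative incidence is (0.693/1.050) × (1 − 0.35) = 42.9%. The excess is 50 − 42.9 = 7.1 points.

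Excess in percentage points over the assumed range:

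| Competing events at 12 months | Net conversion 30% | 50% | 70% |
|---|---|---|---|
| 10% | 1.4 | 2.3 | 2.9 |
| 20% | 2.9 | 4.6 | 5.9 |
| 30% | 4.5 | 7.1 | 9.1 |
| 50% | 7.9 | 12.5 | 16.1 |
| 65% | 10.9 | 17.2 | 22.2 |

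The direction does not depend on these inputs. If no conversion follows a death or relapse, the excess is zero; if one does, it is positive.

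**The case against.** **The estimator is inferred.** Kaplan-Meier is named for EFS, OS and RFS only, so a reader should not take it as prescribed here. That stands. It does not remove the problem, because censoring rules serve a survival-type method, and a cumulative incidence estimator with these patients coded as censored reduces to one minus Kaplan-Meier. The coding is the defect.

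**The rule does not mention death or relapse.** It speaks of patients still MRD positive at the analysis. Censoring the others is the default reading, since Section 6.3.3 offers no alternative.

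**Treatment failure.** A reader might infer that every treatment failure is a competing event as well. The documents do not support that. In Section 6.3.2, failure means not reaching CR, CRi, CRp or CRh, which taken literally includes MLFS. Yet Sections 3.1.2.2 and 3.1.3 let patients transplanted in MLFS go on to maintenance, and Appendix 1, Table 3 schedules marrow MRD for them at the first month and every 3 months. They can still convert under observation, and closing them out at failure would bias the estimate downward. Table 5, note a, also sends patients who stop for reasons other than morphologic relapse to follow-up with 6-monthly marrow. Section 4.5.6 describes that marrow for patients in remission, so how far it applies to failures is unclear. In the post-consolidation cohort the question does not arise, because EFS there has only relapse and death as events.

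**MRD results in general.** A reader might infer that all MRD results are inflated. They are not. Section 6.3.2 analyses MRD negativity at the end of induction, and conversion at any time during treatment in the post-consolidation cohort, as simple proportions with exact intervals.

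**Ranking of cohorts.** It is tempting to call the bias worst in the high-risk cohort, where CR of at most 50% to 55% is expected under standard care. The bias also needs later conversions, and no conversion rates by cohort are given.

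**Conclusion.** The point holds for death and hematologic relapse. Coded as Section 6.3.3 directs, a survival-type estimate of time to MRD-negative status overstates the probability of converting whenever conversions occur later, and the median comes too early.

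The size cannot be fixed from the documents. It is about 1 to 22 percentage points for 30% to 70% net conversion and 10% to 65% competing events at 12 months, under constant hazards. No single value in that range should be read as the expected bias.

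The consequence is limited. The endpoint is exploratory, Section 6.8 calls the study hypothesis-generating, no decision rule uses this endpoint, and the primary CR proportion and secondary MRD proportions are untouched. It is worth correcting because the error has a known direction and a few early deaths among 20 or 30 patients can move the curve visibly.

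**What to change.** Reword Section 6.3.3, or the separate analysis plan, as follows:

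1. Report the Aalen-Johansen cumulative incidence of MRD negativity in all treated patients.
2. Treat death and hematologic relapse before MRD negativity as competing events.
3. Treat treatment failure as a competing event only when the patient leaves study treatment because of it. Do not apply it to patients in MLFS who go on to allo-HSCT and maintenance with continued MRD sampling. State how MLFS stands against the definition of failure, so that the coding is fixed in advance.
4. Drop Day 1 censoring for patients who die, or fail in the sense of item 3, before a first post-baseline MRD sample. Count the competing event at its date.
5. Censor only patients who are alive, free of these events and still MRD positive.

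The cost is wording and a few lines of code. Failure, relapse and death dates are already needed for EFS and OS, and Section 4.6.1 already requires the primary reason for stopping study medication to be recorded. No new data are needed.

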6.4 SAFETY ANALYSES

The safety analysis population will consist of all randomized patients who received at least one dose of any study drug, given in combination or as a single agent.

All verbatim adverse event terms will be mapped to MedDRA thesaurus terms, and adverse event severity will be graded according to NCI CTCAE v5.0.

Safety will be determined using incidence rates for adverse events including mortality, adverse event severity, seriousness, adverse events leading to discontinuation, abnormalities of clinical laboratory tests, and vital signs. Incidence of clinically significant ECG abnormalities will be reported in patient listings and change from baseline summarized. ECG QT and QTcF intervals will be summarized using descriptive statistics.

Exposure to study medication will be summarized by total duration of study medication, number of cycles started and cumulative dose using descriptive statistics.

The number and proportion of patients reporting each symptom (nausea, vomiting, and diarrhea) on the PRO-CTCAE and the change from baseline by category ("frequency," "severity," "interference") will be reported at each assessment timepoint. A summary of

the maximum post-baseline score and change from baseline will also be provided. Graphical representation of PRO-CTCAE items over time may be provided. PRO-CTCAE analyses will be presented separately from the safety analyses.

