3.1.2.1 Definition of DLT

In this study, a DLT is defined as at least one of the following events occurring during the first induction cycle of treatment and assessed by the investigator as clearly not attributable to the patient's underlying disease or concurrent medications:

- Any Grade 5 adverse event unless unequivocally due to the underlying malignancy or extraneous causes
- Any clinically significant, non-hematologic adverse event Grade ≥ 3 unless clearly unrelated to the treatment (except GI toxicity, fatigue, anorexia, and alopecia)
- GI toxicity: nausea, vomiting and/or diarrhea if Grade ≥ 3 severity despite adequate supportive care measures (>72 hours of treatment, requiring tube feeding, total parenteral nutrition, or requiring or prolonging hospitalization) which is attributable to study treatment
- Grade 3 AST or ALT toxicity lasting for >7 days, or Grade 4 lasting for any duration of time not attributable to disease progression
- Prolonged myelosuppression: hypocellular ($\leq 5\%$ cellularity) bone marrow without evidence of leukemia, lasting >28 days from first observation (i.e., the first post-treatment bone marrow examination showing $\leq 5\%$ cellularity or aplasia [Kantarjian et al. 2007])

Other toxicities that are considered clinically relevant and related to study treatment as determined by the investigator and the Medical Monitor may also be considered DLTs.

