4.4.2 Prohibited Therapy

Use of the following therapies (excluding protocol-specified treatments) is prohibited during the study:

- Any anti-cancer therapy, approved or investigational, other than intrathecal CNS prophylaxis (except during HSCT consolidation)
- Hormonal therapy other than contraceptives, stable hormone-replacement therapy, or megestrol acetate
- Biologic agents other than hematopoietic growth factors

MDM2 antagonists were shown in vitro to affect all types of hematopoietic progenitors, including megakaryocytic differentiation. They inhibit both early and late stages of megakaryopoiesis, including ploidy and proplatelet formation (Mahfoudhi et al. 2016). As a consequence, the effect on early progenitors might induce long-lasting thrombocytopenia in vivo.

Therefore, because of the potential severity and duration of thrombocytopenia induced by study treatment, patients in clinical need of chronic treatment with oral or parenteral anticoagulant/antiplatelet agents (e.g., warfarin, chronic daily treatment with aspirin [> 325 mg/day], clopidogrel, dabigatran, apixaban, rivaroxaban, and systemic low-molecular weight heparin), or subcutaneous anticoagulant prophylaxis) are excluded from this study. For patients considered eligible for the study because they are able to tolerate interruption of anticoagulant or antiplatelet treatment, these agents must be discontinued 7 days (or 5 half-lives, whichever is shorter) prior to initiating study treatment (except used as flushes for indwelling catheters). After the study treatment completion or discontinuation visit, treatment with anticoagulant/antiplatelet agents may be re-initiated for patients with transfusion-independent adequate platelet levels as clinically indicated. An exception can be made for patients with stable blood parameters in need of prophylaxis or after consultation with the Medical Monitor if use is clinically needed. The maintenance of anti-thrombotic treatment should be continuously reassessed. Sustained use over time must be clinically warranted.

Oral or parenteral use of the following drugs will be prohibited during the treatment phase in order to prevent undesirable drug–drug interactions (DDIs).

- Strong/moderate inducers or inhibitors of CYP2C8, including gemfibrozil, which is also an inhibitor of UGT1A3 (see [Appendix 17](#), Table 1)
- CYP2C8 (see substrates or OATP1B1/3 substrates (see [Appendix 17](#), Table 3)

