5.1.2 Risk of Overlapping Toxicities

Overlapping toxicities from the combined administration of cytarabine, daunorubicin and idasanutlin are anticipated during study treatment phase. These toxicities include myelosuppression (thrombocytopenia, neutropenia, and febrile neutropenia), infectious complications, and GI disorders (diarrhea, nausea and vomiting; see [Table 7](#)).

Table 7 Overlapping Toxicities Grade \geq 3: Idasanutlin, Cytarabine, and Daunorubicin

| Adverse Events | | 7+3 ^a | Idasanutlin ^b |
|------------------------|---------------------------------|------------------------------------|--------------------------|
| Hematologic toxicities | Thrombocytopenia | 98% | 24.5% |
| | Neutropenia/febrile neutropenia | 91%/35% | 12.4%/26% |
| | Anemia | 76% | 18.2% |
| Infections | Infections (SOC) | 49%–73.7% (<60 yr) 86% (>60 yr) | 30.2% |
| GI toxicities | Diarrhea | 10.8% | 13% |
| | Nausea/vomiting | | 4%/1.3% |

7 + 3 = 7 days of cytarabine plus 3 days of daunorubicin; AML=acute myeloid leukemia; GI=gastrointestinal; R/R=relapsed or refractory; SOC=system organ class.

^a Fernandez et al. 2009; Löwenberg et al. 2009; Lee 2011.

^b Idasanutlin Investigator’s Brochure, Version 10. Cumulative incidences across all solid tumor and R/R AML studies (except GH29914).

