Appendix 1: Schedule of Activities (cont.)

Table 1: Induction (cont.)

MUGA=multiple-gated acquisition (scan); PK=pharmacokinetic; PO=orally; PRO=patient-reported outcome; PRO-CTCAE=Patient-Reported Outcomes Common Terminology Criteria for Adverse Events; QD=once a day; RBR=Research Biosample Repository; TB=tuberculosis.

- ^a The screening period starts with the signing of the Informed Consent Form, including the optional Informed Consent Form if appropriate. Results of standard-of-care tests or examinations performed prior to obtaining informed consent and within the defined window may be used as screening and baseline assessments; such tests do not need to be repeated for screening purposes.
- ^b Informed consent must be documented before any study-specific screening procedure is performed.
- ^c Must be performed within 7 days of the planned D1
- ^d If a chest CT is performed up to 28 days prior to study drug administration, a chest X-ray is not required. Patients with a medical history of fungal and TB infections should have a chest CT performed within 28 days prior to study drug administration.
- ^e Vital signs include body temperature, systolic and diastolic blood pressure, pulse rate and respiratory rate. Body surface area will also be measured at screening.
- ^f Should Day 28 not be the last day of the cycle the following will be assessed every 7 days following D28 until end of cycle: biochemistry, hematology, vital signs, ECOG performance status. Bone marrow, HMRA and whole blood sampling should be repeated on the last day of the cycle with D56 as the limit and if not performed within the previous 2 weeks.
- ^g All ECGs should be performed within 2 hours prior to idasanutlin administration and 6 hours after idasanutlin administration.
- ^h Includes systems of primary relevance (e.g., cardiovascular and respiratory systems), systems associated with symptoms (newly emergent or monitored from baseline), and areas associated with tumor assessment (lymph nodes, liver, spleen, and any other areas identified at baseline). Record new or worsened clinically significant abnormalities on the Adverse Event eCRF.
- ⁱ Includes hepatitis B surface antigen, total hepatitis B core antibody, and hepatitis C virus antibody.
- ^j All hematology and biochemistry assessments may be performed up to 3 days prior to the scheduled timepoint. Results must be reviewed by the investigator (or designee) prior to study drug administration.

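### Prolonged thrombocytopenia is a named risk, but Section 6 plans no analysis of cytopenia duration or count recovery, and in induction Grade ≥3 incidence has almost no room to rise

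*Combined protocol and SAP*

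**What the plan says.** **The risk.** Section 4.4.2 reports in vitro effects of MDM2 antagonists on platelet formation and says that "the effect on early progenitors might induce long-lasting thrombocytopenia in vivo". It then excludes patients who need chronic anticoagulant or antiplatelet treatment, "because of the potential severity and duration of thrombocytopenia induced by study treatment".

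**The background.** Table 7 (Section 5.1.2) sets Grade ≥3 rates with 7+3 beside those with idasanutlin: "Thrombocytopenia | 98% | 24.5"%, "Neutropenia/febrile neutropenia | 91%/35% | 12.4%/26"% and "Anemia | 76% | 18.2"%. Section 5.1.1.2 adds that leukemia patients are already neutropenic and thrombocytopenic at baseline.

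**The analysis.** Section 6.4 states: "Safety will be determined using incidence rates for adverse events including mortality, adverse event severity, seriousness, adverse events leading to discontinuation". Laboratory abnormalities and vital signs follow in the same list. Nothing in Section 6 covers duration of cytopenia, time to neutrophil or platelet recovery, or transfusion independence.

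**The data.** Appendix 1 schedules hematology on Days 1, 2, 5, 8, 15, 22 and 28 of induction and consolidation cycles. If an induction cycle runs past Day 28, "the following will be assessed every 7 days following D28 until end of cycle: biochemistry, hematology"; consolidation has a similar weekly rule. Section 5.5.1 asks for weekly counts until hematologic events resolve and for resolution dates. Section 4.4 records blood products as concomitant therapy.

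**The concern.** Where almost every patient reaches Grade ≥3 on the backbone alone, an added drug can do its hematologic harm by lengthening the cytopenia, and a count of affected patients does not move. The protocol names exactly that possibility, and it manages patients partly by time to recovery: Table 9 branches at 21 and 28 days, Table 12 at 14 days. The planned safety tables have no time axis.

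Two uses of the data are affected. The RP2D takes all safety data into account (Section 3.1.2), so recovery time by dose is relevant to it. The primary endpoint also depends on recovery: CR in Appendix 19 needs ANC ≥1.0 and platelets ≥100 x10^9/L, so slow recovery can lower the CR proportion with no loss of antileukemic effect.

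**Working it through.** **1. Check of the interval method.** Table 7's 98% is a literature figure with no inputs in the documents, so it cannot be recomputed. The plan's exact 90% Clopper-Pearson method can be. Tables 14 and 15 reproduce at N=20: 12 responders 39–78%, 13 44–82%, 14 49–86%, 15 54–90%, 16 60–93%, 17 66–96%, 18 72–98%. Section 6.4 states no interval for safety rates, so the same method is applied below.

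**2. Thrombocytopenia in induction.** Inputs: background p = 0.98 (Table 7); N = 20 per expansion cohort, 40 for both (Section 6.1).
- Expected cases: 20 × 0.98 = 19.6; 40 × 0.98 = 39.2.
- Largest possible rise: 2 percentage points, or 20 × 0.02 = 0.4 of a patient per cohort.
- Chance that all are affected with no added effect: 0.98^20 = 0.67; 0.98^40 = 0.45.
- Lower 90% limit if all are affected: 0.05^(1/20) = 86.1%; 0.05^(1/40) = 92.8%. Both lie below 98%, so no result excludes the background.
- N needed for an all-affected result to exclude 98%: ln 0.05 / ln 0.98 = 148.3, so 149.

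**3. The other lineages.**
- Neutropenia (91%): 18.2 expected of 20, and no result at N=20 excludes 91%. At N=40 only 40/40 does, and 0.91^40 = 0.023.
- Anemia (76%): 19/20 or 36/40 would exclude it, so this is not a ceiling.
- Table 7's 7+3 column does not cover consolidation or single-agent maintenance. The idasanutlin figure for thrombocytopenia is 24.5%.

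**4. Can a duration measure inform at N=20?** The documents give no recovery times, so these are assumptions.
- Share with prolonged Grade ≥3 thrombocytopenia, against an assumed reference of 10%, 20% or 30%: the 90% interval excludes the reference from 5, 8 or 10 patients of 20. The chance of that is 76%, 58% or 59% if the true share is 20 points higher, and 95%, 87% or 87% if it is 30 points higher.
- Median time, assumed log-normal with a 28-day median: SE of the log median = 1.253 × SD / √n, and the 90% factor is exp(±1.645 × SE). With n = 20 and log-SD 0.25, 0.35 or 0.50, the intervals are about 25–31, 24–33 and 22–35 days. If only 10 patients recover and the log-SD is 0.50, the interval is about 20–39 days.

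**5. What the other planned items measure.**
- DLT (Section 3.1.2.1): "hypocellular ($\leq 5\%$ cellularity) bone marrow without evidence of leukemia, lasting >28 days", in the first induction cycle. It has no blood-count criterion.
- CR against CR/CRi/CRp and CR/CRh (Section 6.3.2): status at the end of induction, in patients who otherwise meet the CR criteria; nothing for consolidation.
- Discontinuations and flagged dose modifications (Sections 6.2 and 6.4): these show when a management threshold was crossed, not how long recovery took.
- Change from baseline in targeted laboratory results (Section 2.1): no parameters or timepoints are given.
- Exposure–safety exploration of acute versus delayed cytopenia (Section 3.3.3): serious events, and only if relevant.

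**The case against.** The strongest reply is that delayed recovery would not be invisible. A reader might infer that a low CR rate from inefficacy could not be told from one caused by myelosuppression. The documents do not support that. CR/CRi/CRp and CR/CRh are planned with the same intervals, and Appendix 19 separates them from CR by counts alone. A low CR proportion beside a high CR/CRi/CRp proportion points to incomplete recovery. Marrow and response assessment may also be repeated up to Day 56 of induction, so slow recovery before then can still count as CR.

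A reader might also infer that prolongation would go unreported. That too goes beyond the text. Table 9 turns long delays into dose reductions or discontinuations, which are reported, and resolution dates are captured. The DLT definition leaves room for other clinically relevant toxicities, and Section 3.1.2.2 lets toxicity after the first cycle inform the MTD.

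A third inference, that idasanutlin is expected to delay recovery, is stronger than Section 4.4.2, which says only that it might. Section 5.1.1.2 reports mostly reversible cytopenias in solid tumors and normal marrow recovery in responding AML patients.

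All of this stands and limits the point. None of it yields an estimate of duration or recovery time. The study is also non-randomized and hypothesis-generating, and no 7+3 recovery time is given for comparison. That rules out attribution, but the planned incidence tables share this limit.

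**Conclusion.** The point holds in a limited form. A risk defined partly by duration has no duration or recovery analysis, although serial counts, resolution dates and transfusions are collected. In induction, Grade ≥3 thrombocytopenia incidence cannot carry the signal at N=20 or N=40, and neutropenia incidence can do so only at 40/40. The ceiling should not be extended to anemia, consolidation or maintenance; the documents show none there.

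The ceiling result rests on Table 7's 98% and 91% applying to these patients. At N=20, 20/20 could exclude only a background below 86.1%. The claim that a time measure is more informative rests on assumed spreads and reference shares. It weakens if few patients recover: Section 6.1 expects a CR proportion of up to 50%–55% in high-risk patients under 7+3. This is a worthwhile, low-cost improvement to the safety analysis. It does not invalidate the primary analysis.

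**What to change.** Add to Section 6.4 a descriptive summary by cohort, dose and cycle, for each induction and consolidation cycle:

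- Time from Day 1 to ANC ≥0.5 and ≥1.0 x10^9/L and to platelets ≥50 and ≥100 x10^9/L, the Appendix 19 cut-points. Count recovery after the cycle nadir, because a patient may start consolidation already above them.
- Do not count transfusion-supported platelet values as recovery, and state in advance the transfusion-free interval that applies.
- Cumulative incidence of recovery, with death, persistent leukemia or relapse, and start of the next cycle, transplant or new therapy as competing events.
- The proportion unrecovered at landmarks that fit the schedule, for example Days 42 and 56 in induction and Days 42 and 49 in consolidation. Appendix 1 sets Day 56 and Day 49 as the limits for repeating the end-of-cycle response assessment.

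The cost is analysis wording and one set of tables, with no new visits, samples or change to treatment. The limits should be stated with the tables: recovery dates resolve to about 7 days, precision at N=20 depends on the spread and on how many recover, and attribution to idasanutlin would need an external reference that the documents do not supply.
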